1.2 Rationale for this Study

As described above, vaginal dryness, dyspareunia, and decreased libido are common complaints among breast cancer patients treated in our clinic. With increasing use of aromatase inhibitors which are associated with a higher rate of vaginal dryness than tamoxifen, these problems are becoming even more prominent. Medical oncologists at UCSF do not recommend the use of oral or vaginal cream forms of estrogen replacement therapy in breast cancer patients. However, given the minimal estrogen absorption that has been documented with treatments like the ESTRING, breast cancer physicians at UCSF support the use of certain preparations of intravaginal estrogen for breast cancer patients suffering from severe vaginal dryness or sexual dysfunction resulting in significant decreases in quality-of-life. Based on available evidence, we generally recommend the ESTRING **or** a specially compounded 1% testosterone cream as an initial intervention for urovaginal symptoms. Since loss of libido is increasingly common in this patient population, testosterone cream may offer some benefit in addition to relief from vaginal dryness, although the actual amount of systemic absorption of vaginal testosterone cream is unknown. If patients do not have sufficient symptomatic relief with the initial intervention, patients are then prescribed the alternate treatment.

In severe cases when both these treatments have failed, patients may be offered the Vagifem insert, and their serum estradiol levels are followed carefully to assure that they remain in the postmenopausal range. In the context of recent studies demonstrating elevations in serum estradiol levels to outside the post-menopausal range within two weeks after the initial treatment with the Vagifem insert, patients are counselled that the significance of this transient elevation of estradiol is unknown. Patients are advised that ongoing systemic estrogen absorption is believed to be low with both the ESTRING and the Vagifem insert, but there are no data on the routine use of these treatments in breast cancer patients and how they may impact breast cancer recurrence.

This study will evaluate the safety and tolerability of the ESTRING and 1% testosterone cream administered vaginally as treatments for vaginal dryness and/or decreased libido in women receiving an aromatase inhibitor for Stage I-III breast cancer. This study will serially measure serum estradiol and testosterone levels in breast cancer patients being treated the ESTRING and 1% testosterone cream. The primary objective is to evaluate the safety of these treatments by determining whether an unacceptable number of patients receiving either of these treatments are found to have serum estradiol level outside of the post-menopausal range using standard clinical laboratory measurements. This study will also explore whether either of these treatments are effective in improving gynecologic or sexual quality of life in this patient population. This study may answer a number of important questions regarding these therapies which have not been well-investigated. If either of the treatments is found to be effective, and their short term safety and tolerability are confirmed in this study, further examination into the management of the difficult and increasing problem of urogenital atrophy and decreased libido in breast cancer survivors will be encouraged. Furthermore, improvements in the management of side effects associated with aromatase inhibitor treatment should lead to improved patient compliance, decreased discontinuation of treatment, and better outcomes.

2. STUDY OBJECTIVES

2.1 Primary Objective

To evaluate the safety, based on serial measurements of serum estradiol levels, of intravaginal testosterone cream or the ESTRING administered for relief of vaginal dryness and/or decreased libido related to aromatase inhibitor therapy in early breast cancer patients.

2.2 Secondary Objectives

1. To document the systemic estradiol and testosterone levels at several time points in early breast cancer patients on aromatase inhibitors and being treated with intravaginal testosterone cream or the ESTRING.
2. To compare standard clinical laboratory measurements of serum estradiol with values of serum estradiol as measured by an ultrasensitive assay in a research laboratory.
3. To evaluate changes in gynecologic and sexual quality of life using validated questionnaires (the CARES Sexuality Subscales) in early stage breast cancer patients using intravaginal testosterone cream or the ESTRING for relief of vaginal dryness and/or decreased libido related to aromatase inhibitor therapy.

3. STUDY PLAN AND PROCEDURES

3.1 Overall study design

This will be a single institution open label randomized Phase II study evaluating intravaginal testosterone cream vs. the Estring for vaginal dryness and/or decreased libido in early breast cancer patients treated with an aromatase inhibitor. Up to 80 early stage breast cancer patients will be enrolled over 36-48 months in order to have a total of 70 evaluable patients. To be considered evaluable, patients must complete their baseline evaluation and week 4 safety blood draw. Randomization of patients will attempt to balance the number of patients in each group based on self reported or medically documented depression, use of antidepressants, and relationship status (single vs. partnered). Patients will be randomized to a 12 week course of treatment with either:

- Testosterone Cream 1% micronized in velvachol - 0.5 gm of cream vaginally 3 times a week for total of 12 weeks of treatment
- Estring 2mg ring inserted vaginally once every 12 weeks

Patients will complete quality of life surveys including the CARES Sexual Interest and Sexual Dysfunction Subscales (Appendix A), which includes a single item sexual satisfaction measure previously tested by Ganz, at day 1 (baseline), week 4, and at the end of week 12 (the survey may be done either in the clinic, or at home and then mailed/faxed). Patients will undergo a gynecologic exam at baseline and at the end of week 12 (or sooner if they withdraw from the study or experience unexpected side effects). During this exam, the vaginal epithelium will be assessed using a 3-point scale evaluating color, petechiae, friability and dryness (Appendix B). Within each treatment group, composite scores of the vaginal epithelium at baseline will be compared to composite scores at study termination.

Serum estradiol assays sent to the UCSF clinical laboratory are sent out to Quest Diagnostics, which uses extraction chromatography RIA for their ultra-sensitive estradiol. Day 1 and week 4 samples will also be stored temporarily and then sent in batches to a specialized research lab which has developed an assay to quantify low levels of estradiol found in post-menopausal women. This assay is a radioimmunoassay after ether extraction, and has a sensitivity limit of 3pmol/l. Serum testosterone levels will also be sent to Quest, which uses an ultrasensitive testosterone measurement which is run by liquid chromatography tandem mass spectrometry.

The primary outcome variable in this study is the number of breast cancer patients being treated with either intravaginal testosterone cream or the ESTRING for a 12 week period who are found to have a persistently elevated serum estradiol level outside the post-menopausal range as defined by:

1. An elevation of serum estradiol outside of the post-menopausal range and at least 10 pg/ml higher than the baseline value on two consecutive collections at least four weeks apart.
The post-menopausal range at UCSF is ≤ 10 pg/ml (as measured by Quest Diagnostics, the lab utilized by the UCSF clinical laboratory).

2. If a patient's baseline (day 1) serum estradiol level is >10 pg/ml, the subsequent levels must be >10 pg/ml higher than the baseline value to be considered a significant elevation outside the post-menopausal range.

A secondary outcome variable is the change in scores on the CARES Sexual Dysfunction Subscale from baseline to week 12. The ESTRING and testosterone cream treatment groups will be analyzed independently.

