3.3.6 Replacement Policy

Patients who do not initiate study assigned therapy after signing consent or do not complete the week 4 blood draw for safety evaluation will be considered unevaluable and will be replaced.

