7. STATISTICAL METHODS AND DETERMINATION OF SAMPLE SIZE

7.1 Description of outcome variables in relation to objectives and hypotheses

The primary outcome variable for determining safety in this study is the number of breast cancer patients being treated with either intravaginal testosterone cream or the ESTRING for a 12 week period who have a persistently elevated serum estradiol level outside the post-menopausal range (as defined in section 3.1).

The test statistic is the number of patients that have a persistently elevated estradiol level above the post-menopausal range as described above. In the medical literature, there are no data to suggest what is “safe” or “unsafe” in terms of postmenopausal breast cancer patients being exposed to levels of estrogen above the postmenopausal range for a short duration of time (such as 12 weeks). No data exist to suggest that short term exposure to levels of estrogen above the post-menopausal range for up to 12 weeks would impact breast cancer recurrences. Therefore, it is fairly arbitrary to conclusively state that a certain rate of patients experiencing a short term increase in estradiol exposure with either of the treatment interventions (ESTRING or testosterone cream) is safe or unsafe. Taking this into consideration, we will consider each intervention “safe” if no more than 25% of patients in that arm have persistently elevated serum estradiol levels above the postmenopausal range after exposure to either of the study interventions.

The trial is designed to test the null hypothesis that a treatment is unsafe (25% or more of patients have a persistently elevated estradiol above the postmenopausal range) at a 5% level of significance. The alternate hypothesis is that a treatment is safe (i.e. fewer than 25% of patients have a persistently elevated estradiol above the postmenopausal range). Each treatment arm is tested separately. The trial is designed to have 98% power of concluding that a treatment is safe if the true failure rate is 5% and 70% power when the true failure rate is 10%.

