7.2 Interim Analysis / Stopping Rule

This will be a two stage study. In stage 1, ten patients are enrolled in each arm. If 3 or more of the first 10 patients in an arm fail (i.e. have a “persistently elevated estradiol level” as defined in Section 3.1 Study Design), no more patients are enrolled in that arm and it is concluded that the treatment for that arm is not safe. Patients already enrolled in that arm will be notified and given the option of discontinuing treatment. In stage 2 an additional 25 patients are enrolled in the arms that were not closed after stage 1. A treatment is considered unsafe if a total of 5 or more patients in both stages have failed (i.e. have a “persistently elevated estradiol level” as defined above). Under the null hypothesis that the treatment is unsafe with true probability of failure (i.e. persistent elevation of estradiol above postmenopausal threshold) equal to 25% or greater, the probability of rejecting the null hypothesis falsely (i.e. concluding the treatment is safe when it is not) is 5%. Figure 1 shows the operating characteristic using this two stage design.

[figure not shown]

Figure 1. Operating characteristic for two-stage safety trial.

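### A patient becomes evaluable on one post-baseline estradiol draw, but failure needs two, so an evaluable patient without a usable second draw cannot count against safety and is not replaced

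*Protocol*

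**What the plan says.** **Evaluability.** Section 3.1: "To be considered evaluable, patients must complete their baseline evaluation and week 4 safety blood draw".

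**Replacement.** Section 3.3.6 covers two groups: patients who do not start the assigned therapy, and those who "do not complete the week 4 blood draw for safety evaluation will be considered unevaluable and will be replaced". Nobody else is replaced.

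**Failure.** Section 3.1 defines a persistent elevation as estradiol outside the postmenopausal range and at least 10 pg/ml above baseline "on two consecutive collections at least four weeks apart". The Safety part of the synopsis adds that the baseline value is not one of the two. The table in section 3.2 puts the first post-baseline draw at week 4.

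**Decision.** Section 7.2 stops an arm under this rule: "If 3 or more of the first 10 patients in an arm fail". Otherwise 25 more patients are enrolled, and the arm is unsafe if 5 or more of the 35 have failed. Section 7.1 takes a failure rate of 25% or more as the null hypothesis.

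**Draws that could supply the second value.** Section 3.2 schedules week 12, a repeat within 4 to 6 weeks of an abnormal week-4 or week-12 result, and a hormone measurement at early withdrawal. Section 3.3.5 asks patients who stop early to attend a termination visit with the week-12 assessments.

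**The concern.** At the moment a patient becomes evaluable she has one post-baseline value, and one value can never meet the failure definition. If no usable second value follows, she stays among the 35, adds nothing to the failure count, and section 3.3.6 gives no route to replace her. This affects a patient who is elevated at week 4 and has no later draw. It also affects one who is normal at week 4 and has no later draw, and one whose first elevation is her last sample.

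The direction matters because the burden of proof is on safety. The limits of 3 in 10 and 5 in 35 were set for patients who can all be seen to fail. Fewer patients able to fail against the same limits makes it easier to reject the null hypothesis that the treatment is unsafe, and that is the trial's primary conclusion.

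**Working it through.** **Inputs** (sections 7.1 and 7.2): null failure rate 25%; stage 1 has 10 patients per arm and stops at 3 or more failures; stage 2 adds 25; the arm is safe if total failures are 4 or fewer; stated false-safe probability 5%; stated power 98% at a true 5% rate and 70% at a true 10% rate.

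**Step 1: the plan's own figures.** For a failure rate p,

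P(safe | p) = Σ over x = 0, 1, 2 of P(X₁ = x) × P(X₂ ≤ 4 − x), with X₁ ~ Bin(10, p) and X₂ ~ Bin(25, p).

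At p = 0.25: 0.0563 × 0.2137 + 0.1877 × 0.0962 + 0.2816 × 0.0321 = 0.0391.

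| True rate | Stated P(safe) | Exact P(safe) |
|---|---|---|
| 25% | 5% | 3.9% |
| 5% | 98% | 96.4% |
| 10% | 70% | 71.4% |

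The two powers agree with the stated ones to within 2 percentage points. The false-safe rate is below 5% rather than equal to it. That difference is conservative and separate from this point, but it sets the margin available: 3.9% against 5%.

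**Step 2: unconfirmed failures.** Assumption, not in the protocol: a share m of true failures has no usable second draw, and these patients remain in the 35 as non-failures. The rate that the rule sees is then 0.25 × (1 − m).

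| m | Rate seen | False-safe probability | Chance that stage 1 stops the arm |
|---|---|---|---|
| 0 | 25.0% | 3.9% | 47.4% |
| 5% | 23.75% | 5.5% | 43.7% |
| 10% | 22.5% | 7.6% | 39.8% |
| 20% | 20.0% | 13.8% | 32.2% |

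The false-safe probability passes 5% at m of about 3.6%.

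**Step 3: the same in whole patients.** If k stage-2 patients are undetermined, stage 2 has 25 − k patients able to fail while the limit of 5 is unchanged. At p = 0.25, k = 1 gives 4.7%, k = 2 gives 5.6% and k = 3 gives 6.6%. One such patient is absorbed by the margin; two are not.

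**Step 4: do the scheduled draws close the gap?** A patient elevated at week 4 who withdraws at week 8 or later and attends the termination visit can be classified as a failure. One whose only further sample is a withdrawal draw less than four weeks after week 4 cannot, however high the value. A withdrawal draw that is itself the first elevation cannot either, unless another sample follows. None of these draws is a condition of evaluability.

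**Step 5: power cost of a conservative classification.** If elevations never followed up are counted as failures and add 1 percentage point to a true 5% rate (an assumption), P(safe | 0.06) = 93.4% against 96.4%. Counting every undetermined patient as a failure would cost far more: with 5% undetermined, the rate seen is 0.05 + 0.95 × 0.05 = 9.75%, and power falls to 73.2%.

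**The case against.** The strongest reply is that the protocol nowhere says a patient without a second draw is a success, and that the coding of missing endpoint data commonly belongs in the SAP. The first part is correct. A reader might infer a stated rule that missing means safe, but there is no such sentence. The result follows only from counting failures against fixed limits among patients already accepted as evaluable. The second part goes only so far. Evaluability, replacement, the endpoint and the decision limits are all fixed in the protocol, and replacement is an enrolment rule that an SAP would not normally rewrite.

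It is also fair to say that the repeat draw, the week-12 draw and the termination visit will settle most cases, and that a failure confirmed by week 8 to 10 is unaffected by later loss. This limits the frequency of the problem but does not remove it.

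Two stronger readings are not supported:

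- A reader might take the allowance of 80 enrolled for 70 evaluable (10/80 = 12.5%) as the plan's own loss rate. That allowance covers patients who are unevaluable as the protocol defines it. They are replaced and do not sit among the 35. It says nothing about loss after week 4.
- A reader might suppose that patients who stop are the likeliest true failures. The protocol does not link stopping to a patient's estradiol result. If loss were concentrated among elevated patients, the inflation would be larger, but that is conjecture.

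**Conclusion.** The point holds: the evaluability and replacement rules do not match the endpoint, and the mismatch can only favour a conclusion of safety. Its direction needs no assumption beyond reading the failure limits as written. Its size does. With 5% to 20% of true failures unconfirmed, the false-safe probability is 5.5% to 13.8% instead of 3.9%, and the 5% level is lost at about 3.6%, or two undetermined stage-2 patients in an arm. If follow-up after week 4 is nearly complete, the stated level survives. Since the loss rate is unknown and the scheduled draws mitigate it, this is a change that should be made rather than a defect that invalidates the design.

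**What to change.** In sections 3.1, 3.3.6 and 7.1, define a patient as evaluable for the primary endpoint only when her failure status is determined from the week-4, week-12, repeat and early-withdrawal draws already scheduled. Place each treated patient who has a week-4 result in exactly one class:

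1. **Failure:** a confirmed persistent elevation at any time or, conservatively for the decision rule, an elevation meeting the criterion whose required repeat was never obtained and which no later draw at least four weeks on resolves. Counted, not replaced.
2. **Non-failure:** week-4 and week-12 results and any triggered repeat available, without meeting the definition.
3. **Undetermined:** no qualifying elevation, but week 12 missing. Replaced under section 3.3.6 as far as the ceiling of 80 allows.

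Report the decision with and without the unconfirmed elevations counted as failures, and the number undetermined by arm.

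**Cost.** Protocol wording and no new procedures. The failure count may be slightly less favourable, with power at a true 5% rate falling to 93.4% under the 1-point assumption above. A few more patients may need replacing; the 10 spare places also have to cover losses before the week-4 draw, so they may not all fit. Replacing undetermined patients restores the 3.9% only if their loss is unrelated to estradiol, which is why their number should be reported.

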Up to 80 patients will be randomized to receive either testosterone or ESTRING so that 35 evaluable patients will receive each treatment. Randomization will attempt to balance the number of patients in each group based on self reported or medically documented depression, use of antidepressants, relationship status (single vs. partnered). Estradiol will be measured at baseline, at 4 weeks, and at 12 weeks into the study. If a patient is subsequently found to have a serum estradiol level outside of the post-menopausal range on day 1 of the study before the intervention begins (despite having a post-menopausal value during screening labs), this patient will be allowed to stay on study, and the subsequent estradiol level must be > 10 pg/ml higher than the baseline value to be considered a significant elevation outside the post-menopausal range. If a patient has an estradiol level outside of the post-menopausal range on the week 4 draw, or if there is a > 10 pg/ml increase in estradiol levels in patients with a baseline value above the post-menopausal range as described previously, they will have an additional lab draw at week 8.

Statistical methods

The primary outcome variable for determining safety at the end of the study is serial serum estradiol measurement. The test statistic is the number of patients that have a persistently elevated estradiol level above the post-menopausal range as described above. In the medical literature, there are no data to suggest what is “safe” or “unsafe” in terms of postmenopausal breast cancer patients being exposed to levels of estrogen above the postmenopausal range for a short duration of time (such as 12 weeks). No data exist to suggest that short term exposure to levels of estrogen above the post-menopausal range for up to 12 weeks would impact breast cancer recurrences. Therefore, it is fairly arbitrary to conclusively state that a certain rate of patients experiencing a short term increase in estradiol exposure with either of the treatment interventions (ESTRING or testosterone cream) is safe or unsafe. Taking this into consideration and after consulting with a number of breast cancer experts, we will consider each intervention “safe” if no more than 25% of patients in each arm have persistently elevated serum estradiol levels above the postmenopausal range after exposure to either of the study interventions.

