Review of the literature on management of vaginal symptoms in post-menopausal women identifies several therapies that appear to be effective in improving or eliminating vaginal dryness and decreasing dyspareunia. Non-hormonal vaginal moisturizers have been shown to relieve urogenital symptoms, but are not as effective as vaginal estrogens in randomized trials (14). A multicenter, open-label, randomized, parallel-group study compared the efficacy and safety of 25-microgram 17beta-estradiol vaginal tablets (Vagifem) with 1.25-mg conjugated equine estrogen vaginal cream (Premarin Vaginal Cream) for the relief of atrophic vaginitis in 159 post-menopausal women (15). Both treatments provided equivalent relief of the symptoms of atrophic vaginitis based on composite scores of vaginal symptoms (dryness, soreness, and irritation). At weeks 2, 12, and 24, increases in serum estradiol concentrations and suppression of follicle-stimulating hormone were observed in significantly more patients who were using the vaginal cream than in those who were using the vaginal tablets ($p < 0.001$). Vaginal tablet therapy resulted in greater patient acceptance and lower withdrawal rates compared with vaginal cream therapy. In a double-blind placebo-controlled, 1612 post-menopausal patients with urogenital complaints were randomized to receive the Vagifem insert or placebo tablet once a day over a period of 2 weeks, and then twice a week for a total of the 12 months (16). The overall success rates of Vagifem vs. placebo on subjective and objective symptoms of vaginal atrophy were 85.5%, and 41.4%, respectively. A significant improvement of urinary atrophy symptoms was also seen in the Vagifem treated group as compared with the beginning of the study (51.9% vs. 15.5%, $P=0.001$). Therapy with the Vagifem insert did not raise serum estrogen level nor stimulated endometrial growth in this study.

An estradiol releasing vaginal ring (Estring) has been compared to a topical estriol cream (Synapause) in a 12 week treatment study in postmenopausal women. The Estring was found to be well tolerated, produced equivalent results in reducing vaginal symptoms, and was preferred by patients as less messy and easier to use (17). Clinical trials with Estring have shown that there is minimal systemic absorption of estradiol and the range of serum estradiol

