Appendix B. Description of the 3-point vaginal epithelium score

A number of vaginal changes occur with loss of estrogen. There is loss of the normal vaginal rugae and the resultant thin epithelium often has visible blood vessels. Petechiae relates to visually apparent spontaneous hemorrhage of these blood vessels within the vaginal epithelium. Friability relates to thin dry vaginal tissues that bleed easily to the touch. The color changes from pinkish to a pale white. Loss of lubrication occurs and the epithelium appears dry. A number of studies evaluating vaginal atrophy have used 3 -5 point scales to assess vaginal health indices. These assessments are not typically validated but allow for objective measurements by a clinician. We have chosen a common 3 point scale to assess the degree of atrophy with numeric values of 0 for none, 1 for mild and 2 for moderate or severe changes. Composite scores at baseline will then be compared to those at study termination.

Descriptive Assessment of Vaginal Mucosa

Vaginal atrophy score				
Signs of atrophy	None*	Mild	Moderate	Severe
Rugae	Normal number and depth	Reduced rugae	Rare rugae	Smooth vagina
Pallor	Normal pink	Light pink	Very pale	White or deep red
Petechiae	None	Bleeds on scraping	Bleeds on contact	Clearly seen
Mucosal thinning (elasticity)	Normal	Decreased	None	Stenosis
Dryness	Normal lubrication	Slightly decreased	Minimal lubrication	Dry

* Normal subject.

[figure not shown]
References of studies that have used similar 3-5 point vaginal assessment scales.

Eisberg et al. Endometrial and Vaginal Effects of low-dose estradiol delivered by vaginal ring or vaginal tablet. Climacteric 2005;8:83-92

Parsons A et al. Effect of Raloxifene on the Response to Conjugated Estrogen Vaginal Cream or Nonhormonal Moisturizers in Postmenopausal Vaginal Atrophy. Obstetrics & Gynecology 2003;101:346-352

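### The vaginal epithelium score is compared only before and after within each arm, so the randomized cream-versus-ring contrast goes unused and the within-arm change cannot be attributed to treatment

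*Protocol*

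**What the plan says.** Protocol section 3.1 describes a gynecologic exam at baseline and at the end of week 12, or sooner on withdrawal, at which the clinician scores the vaginal epithelium. The analysis is given in one sentence: "Within each treatment group, composite scores of the vaginal epithelium at baseline will be compared to composite scores at study termination". Appendix B describes the grading as "numeric values of 0 for none, 1 for mild and 2 for moderate or severe changes", says that such scales are not usually validated, and ends: "Composite scores at baseline will then be compared to those at study termination". No test, significance level or success rule is attached to the score. It does not appear in section 2 (objectives) or in section 7 (statistical methods).

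The design is open label ("This will be a single institution open label randomized Phase II study") with two active arms and no placebo or untreated arm (synopsis: "Up to 80 patients will be randomized to receive either testosterone or ESTRING so that 35 evaluable patients will receive each treatment"). No blinded assessor is mentioned. For the CARES Sexual Dysfunction Subscale, by contrast, section 7.3 plans both a paired comparison within each arm and a two-sample comparison of change between arms.

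**The concern.** Both randomized arms are scored at baseline and at termination, so a randomized comparison of the two products on atrophy is available from data already collected. The protocol names only the comparison that randomization does not protect. A before-and-after change in one arm combines any drug effect with placebo response, an unblinded clinician's expectations, and some regression to the mean in women who enter because of current complaints.

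The score matters because vaginal dryness is part of the title indication, and this is the only clinician-assessed measure of atrophy. The CARES Sexual Dysfunction Subscale in Appendix A has one lubrication item out of four. Section 1.2 looks ahead to what follows "If either of the treatments is found to be effective, and their short term safety and tolerability are confirmed in this study". A before-and-after result on this score could not carry such a finding. The protocol's own background shows that improvement without active drug can be large. In a placebo-controlled trial of a vaginal estradiol tablet it reports: "The overall success rates of Vagifem vs. placebo on subjective and objective symptoms of vaginal atrophy were 85.5%, and 41.4%, respectively".

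**Working it through.** **1. The nearest stated figure.** No power or sample size is given for the epithelium score. The only powered before-and-after symptom analysis is the CARES paired test in section 7.3 (35 per arm, SD 1.17, correlation 0.8, change 0.41, two-sided 5%, stated power 90%).

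- SD of difference = √(2 × 1.17² × (1 − 0.8)) = √0.548 = 0.740.
- Power is 0.890 by the noncentral t and 0.906 by the normal approximation, which agrees with the stated 90%.

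The sample size, level and sidedness used below are borrowed from that test.

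**2. Inputs for the illustration.**

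- n = 35 in one arm (synopsis and section 7.3).
- Two-sided 5% test: an assumption for this score.
- Share improving by one grade, p = 0.414: the placebo success rate in section 1.1, used as a stand-in.
- Share worsening by one grade, q: not given in the protocol, so varied from 0 to 25%.
- Everyone else is unchanged.

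**3. Formulas.**

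- *Sign test, exact.* The number of patients who change is M ~ Bin(35, p + q). Among them the number improving is K ~ Bin(M, p/(p + q)). An improvement is declared when K > M/2 and 2 × P(Bin(M, 0.5) ≥ K) ≤ 0.05.
- *Paired t, simulated (20,000 runs)* on changes of +1, 0 and −1, with mean p − q and variance p + q − (p − q)².

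Hand check of the paired t at q = 0.10: mean 0.314; variance 0.514 − 0.314² = 0.415; SD 0.645; standard error 0.645/√35 = 0.109; ratio 2.88. Against a critical value of 2.03 this gives power of about Φ(0.85) = 0.80. The simulation gives 0.79.

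**4. Chance that an inert product shows a significant within-arm improvement.**

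| Share worsening (assumed) | Sign test | Paired t |
|---|---|---|
| 0% | 99.9% | about 100% |
| 5% | 91% | 95% |
| 10% | 71% | 79% |
| 15% | 48% | 58% |
| 20% | 29% | 38% |
| 25% | 16% | 23% |

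The nominal rate in the favourable direction is 2.5%. When improving and worsening are equally likely (both 0.414), the paired t returns 2.5% and the sign test 1.5%, as they should.

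The chance exceeds 50% only if fewer than about 14.5% worsen (sign test) or about 17% (paired t). If 30% improve and 10% worsen, it is 37% (sign test) and 46% (paired t). Evaluability in section 3.1 requires only the baseline evaluation and the week 4 blood draw, so fewer than 35 may have both exams. With n = 30 the sign test gives 85%, 62%, 41% and 25% at 5, 10, 15 and 20% worsening.

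**5. The between-arm comparison on the same inert data.** Both arms have expected change p − q, so the expected difference is zero. With 35 per arm, a t-test on change is significant in 4.8-4.9% of trials for q from 0 to 20%. Comparing the proportions improved gives 4.7% (pooled z) or 2.7% (Fisher). Change shared by the arms cancels.

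**The case against.** The case against giving this much weight is substantial, and several parts of it stand.

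- **The 41.4% is not a rate for this score.** It is overall success on combined subjective and objective symptoms, in postmenopausal women with urogenital complaints who used the tablet "twice a week for a total of the 12 months" after a two-week daily phase. The score here is a clinician composite of several signs, taken at 12 weeks in women on aromatase inhibitors. A one-grade change of +1, 0 or −1 simplifies it further. This stands, and it makes the table an illustration.
- **A reader might infer that an inert product would usually come out significant.** That depends on the share who worsen, which the protocol does not give. It is true below about 15% and false at 20% or more.
- **A reader might infer that the protocol will credit the change to treatment.** The text does not say so. The score is in no objective and is not a listed outcome variable. Section 1.2 speaks of exploring effectiveness for gynecologic or sexual quality of life, which the third secondary objective measures by CARES. The planned comparison may be meant as descriptive.
- **Some sources of spurious change are weak.** Sections 3.3.3 and 4.5 bar starting moisturizers or changing their use, so constant background use is not an obvious cause of change. Entry is on complaints, which may be decreased libido alone, and not on a score threshold, so regression to the mean is at most indirect.
- **A between-arm test has limits.** It does not remove scoring bias that differs by product, and with two active arms it cannot show that either works.
- **The rest may be in a SAP.** A SAP may exist, section 7.5 restrains formal testing because of multiplicity, and section 7.3 leaves superiority to a larger study. However, the protocol does not leave this analysis open. It names the within-arm comparison, while section 7.3 shows that a between-arm one was considered for CARES.

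**Conclusion.** The point holds in a limited form. The protocol fixes a weaker comparison for its only clinician-assessed measure of atrophy and leaves the randomized contrast on that measure unused. This follows from the text of section 3.1 and Appendix B and does not depend on the simulation. A within-arm change in this open-label trial is not evidence that either product works.

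The size is uncertain. In the worsening scenarios tabulated, the chance of a significant result for an inert product runs from 16-23% up to nearly 100%, always well above 2.5%. It rests on three assumptions that the protocol does not supply for this score: the test and its level, the share improving, and the share worsening. The documents support neither the statement that a false improvement is the usual outcome nor the statement that an efficacy claim from this score is planned. The weight is modest, because the score is a supportive measure outside the primary safety endpoint and the listed objectives.

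**What to change.** In section 3.1 and Appendix B, replace the sentence on composite scores with text to this effect:

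*The composite vaginal epithelium score at study termination (the week 12 exam or the early-withdrawal exam) will be compared between the randomized arms with adjustment for the baseline composite, and the adjusted difference will be reported with its 95% confidence interval. Changes within each arm will be described and will not be taken as evidence that either product is effective, because there is no placebo or untreated arm.*

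Keeping study termination as the time point means that patients who leave early and have the termination exam (sections 3.2 and 3.3.5) stay in the analysis. The choice between a linear and an ordinal model can be left to the SAP.

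The cost is one revised sentence in two places and one more exploratory analysis on data already collected. The result speaks only to cream versus ring and cannot show that either product works.
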